5.4.5.2. Liver Chemistry Testing Procedures

For subjects meeting any of the liver chemistry stopping criteria in Section 5.4.5 make every attempt to carry out the liver event follow-up assessments described below:

- Viral hepatitis serology, including:
 - Hepatitis A IgM antibody
 - Hepatitis B surface antigen and Hepatitis B Core Antibody (IgM)
 - Hepatitis C RNA
 - Cytomegalovirus IgM antibody
 - Epstein-Barr viral capsid antigen IgM antibody (or if unavailable, then obtain heterophile antibody or monospot testing)
- Serum creatine kinase (CK) and lactate dehydrogenase (LDH). Fractionate bilirubin, if total bilirubin ≥ 2 X upper limit of normal (ULN). Obtain a complete blood count (CBC) with differential to assess eosinophilia.
- Record the appearance or worsening of clinical symptoms indicative of hepatitis or hypersensitivity, such as fatigue, nausea, vomiting, right upper quadrant pain or tenderness, fever, rash or eosinophilia as relevant on the AE CRF.
- Record the use of concomitant medications, including acetaminophen, herbal remedies or any other over the counter (OTC) medications, or any putative hepatotoxins, on the concomitant medication CRF.

Every attempt should be made to obtain the following assessments for subjects with ALT ≥ 3 X ULN and bilirubin ≥ 2 X ULN ($>35\%$ direct). These assessments are optional for other abnormal liver chemistries:

- Anti-nuclear antibody, anti-smooth muscle antibody, and Type 1 anti-liver kidney microsomal antibodies.
- Liver imaging (ultrasound, MRI or CT) to evaluate liver disease.
- Serum acetaminophen adduct High Performance Liquid Chromatography (HPLC) assay (quantifies potential acetaminophen contribution to liver injury in subjects with definite or likely acetaminophen use in the preceding week).

5.4.6. Trametinib Dose Modification for Pneumonitis

Pneumonitis has been observed in patients receiving trametinib. To reduce the risk of pneumonitis, patients will be monitored closely for symptoms and evaluated with imaging and functional tests. Dose modification and supportive care guidelines for pneumonitis are described in the tables below.

Pneumonitis Guidelines for Trametinib Monotherapy		
CTCAE Grade	Adverse Event Management	Action and Dose Modification
Grade 1	
 • CT scan (high-resolution with lung windows) recommended. • Work-up for infection • Monitoring of oxygenation via pulse-oximetry recommended • Consultation with pulmonologist recommended 	
 • Continue trametinib at current dose
Grade 2	
 • CT scan (high-resolution with lung windows) recommended. • Work-up for infection • Consult pulmonologist • Pulmonary function tests – if < normal, repeat every 8 weeks until ≥ normal • Bronchoscopy with biopsy and/or BAL recommended • Symptomatic therapy including corticosteroids if clinically indicated 	
 • Interrupt trametinib until recovery to Grade ≤1 • Restart treatment with trametinib dose reduction (25% dose reduction in patients receiving oral solution or specified dose reduction in patients receiving tablets (See Appendix II)) • Escalation to previous dose level after 4 weeks may be considered after consultation with the study chair • If no recovery to Grade ≤1 within 4 weeks, permanently discontinue trametinib
Grade 3	
 • Same as Grade 2 	
 • Interrupt trametinib until recovery to Grade ≤1 • After consultation with the study chair, trametinib may be restarted with a dose reduction (25% dose reduction in patients receiving oral solution or specified dose reduction in patients receiving tablets (See Appendix II)) • If no recovery to Grade ≤1 within 4 weeks, permanently discontinue trametinib
Grade 4	
 • Same as Grade 2 	
 • Permanently discontinue trametinib

5.4.7 Trametinib Dose Modification for Reduced Left Ventricular Ejection Fraction
Decreases of the left ventricular ejection fraction (LVEF) have been observed in patients receiving trametinib. Therefore, ECHO/MUGAs must be performed at baseline, at the end of cycle 1 and at the end of cycle 2. Any ECHO/MUGAs thereafter should be done only if clinically indicated. The same procedure (either ECHO or MUGA, although ECHO is preferred) should be performed at baseline and at follow-up visit(s).

Trametinib Dose Modification Guidelines and Stopping Criteria for LVEF Decrease		
Clinic	LVEF-drop (%) or CTCAE grade	Action and Dose Modification
Asymptomatic	Absolute decrease of >10% in LVEF compared to baseline and ejection fraction below the institution's LLN.	
 • Interrupt trametinib and repeat ECHO/MUGA within 2 weeks.^a • If the LVEF recovers within 4 weeks (defined as LVEF \geqLLN and absolute decrease \leq10% compared to baseline): 
 • Consult with the study chair and request approval for restart. • Restart treatment with trametinib at reduced dose by one dose level.^b • Repeat ECHO/MUGA 2, 4, 8, and 12 weeks after re-start; continue in intervals of 12 weeks thereafter. • If LVEF does not recover within 4 weeks: 
 • Consult with cardiologist. • Permanently discontinue trametinib. • Report as SAE • Repeat ECHO/MUGA after 2, 4, 8, 12, and 16 weeks or until resolution. • Consult with the study chair.^c
Symptomatic^b	
 • Grade 3: resting LVEF 39-20% or \geq20% absolute reduction from baseline • Grade 4: Resting LVEF \leq20%. 	
 • Permanently discontinue trametinib. • Report as SAE. • Consult with cardiologist. • Repeat ECHO/MUGA after 2, 4, 8, 12, and 16 weeks or until resolution.

^a If ECHO/MUGA does not show LVEF recovery after 2 weeks, repeat ECHO/MUGA 2 weeks later.
^b Escalation of trametinib to previous dose level can be considered if LVEF remains stable for 4 weeks after restarting of trametinib. Approval from the study chair is required.
^c Symptoms may include: dyspnea, orthopnea, and other signs and symptoms of pulmonary congestion and edema.

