2.3 Adult Studies

2.3.1 Adult Phase I Studies

A phase 1/2 trial of single agent trametinib in adults with *RAS* mutated, multiply relapsed or refractory myeloid malignancies (n=57) demonstrated a 21% response rate compared with a 3% response rate in patients with *RAS* wild-type or unknown leukemia (n=30). Hepatic toxicities (9%), gastrointestinal disorders (7%) and rash (5%) were the most frequent Grade 3/4 AEs. AEs possibly related to inhibition of MEK signaling were blurred vision (total, 13%; Grade 3, 1%) and decreased cardiac ejection fraction (total, 9%; Grade 3, 6%).²⁷

The Maximum Tolerated Dose (MTD) of trametinib in adults is 3 mg once daily, and the RP2D of trametinib is 2 mg once daily. Five monotherapy studies administered trametinib 2 mg daily to 499 adult subjects. The most common adverse events were rash, diarrhea, fatigue, peripheral edema, nausea, dermatitis acneiform, vomiting, constipation, anemia, pruritus, alopecia, hypertension, decreased appetite, dyspnea and dry skin. In these studies, up to 32% of subjects reported serious AEs (SAEs), and up to 13% permanently discontinued study treatment due to AEs. Rash, diarrhea, visual disorders, hepatic disorders, cardiac-related AEs, and pneumonitis are considered AEs of special interest because they are either known class effects (observed with other MEK inhibitors) or potentially life-threatening.

Cardiac-related adverse events are known to occur in adults treated with trametinib. In a phase 2 trial, patients (n=97) underwent serial assessment of LVEF, three patients (3%) developed asymptomatic and reversible Grade 3 LVEF reduction.²⁸ In a phase 3 trial comparing trametinib versus dacarbazine plus paclitaxel, 14 of the 211 patients who received at least one dose of trametinib developed cardiac-related adverse events (7%), 11 developed decreased LVEF, and three had LV dysfunction.²⁹ Cardiomyopathy resolved in 10 of the 14, but four patients had serious cardiac-related events that were considered to be drug-related and led to permanent discontinuation of the study drug. Across clinical trials of trametinib at the recommended adult dose (2 mg daily), approximately 11% of patients have developed evidence of decrease in LVEF below the institutional lower limits of normal with an absolute decrease in LVEF $\geq 10\%$ below baseline; 5% have developed decrease in LVEF below the institutional lower limits of normal with an absolute decrease in LVEF of $\geq 20\%$ below baseline.³⁰

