4.4 Cycle 3 and All Subsequent Cycles

4.4.1 Therapy Delivery Map – All Subsequent Cycles This therapy Delivery Map (TDM) relates to all subsequent cycles. Each cycle lasts 28 days. Use a copy of this page once for each cycle (please note cycle number below).
	
_____ Patient COG ID number
 
_____ DOB

--	---

Criteria to start each cycle are listed in [Section 3.2.5](#). Treatment details are in [Section 4.4.3](#).

This therapy delivery map is **two (2)** pages in length.

DRUG	ROUTE	DOSAGE	DAYS	IMPORTANT NOTES
Trametinib Do not use commercial supply	PO	Age-based dosing: < 6 years= 0.032 mg/kg/dose ≥ 6 years = 0.025 mg/kg/dose Max dose= 2 mg	Daily	See Appendix II for tablet formulation dosing nomogram.

Enter Cycle #: _____ Ht _____ cm Wt _____ kg BSA _____ m²

Date Due	Date Given	Day	Trametinib mg	Studies
			Enter calculated dose above and actual dose administered below	
		1	_____ mg	a-g
		2	_____ mg	
		3	_____ mg	
		4	_____ mg	
		5	_____ mg	
		6	_____ mg	
		7	_____ mg	
		8	_____ mg	
		9	_____ mg	
		10	_____ mg	
		11	_____ mg	
		12	_____ mg	
		13	_____ mg	
		14	_____ mg	
		15	_____ mg	
		16	_____ mg	
		17	_____ mg	
		18	_____ mg	
		19	_____ mg	
		20	_____ mg	
		21	_____ mg	
		22	_____ mg	
		23	_____ mg	
		24	_____ mg	
		25	_____ mg	
		26	_____ mg	
		27	_____ mg	
		28	_____ mg	h, i [#] , j, k
		29	[#] See note on page 2 of TDM regarding observation i. Following completion of the cycle, the next cycle starts on Day 29 or when starting criteria are met (see Section 3.2.5), whichever occurs later. Please continue onto the next cycle no later than 14 days from the end of the previous cycle.	

See [Section 5.0](#) for Dose Modifications for Toxicities and the COG Member website for Supportive Care Guidelines.

4.4.2 Required Observations in All Subsequent Cycles**Collect observations beginning in Cycle 3.**

- a. Physical exam (including VS) and adverse events
- b. Concomitant medications
- c. Performance status
- d. CBC, differential, platelets
- e. Electrolytes including Ca^{2+} , Mg^{2+} , and PO_4 , BUN and creatinine, creatinine kinase, Total and direct bilirubin, AST, and ALT

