- f. Dermatologic exam. Performed by the investigator (or dermatologist, at the discretion of the investigator). If possible, the same physician should perform each exam throughout the study. Photographs of suspect lesions at baseline are recommended with photographs and/or biopsies of any new or changing lesions recommended at subsequent on-study visits
- g. Collect a peripheral blood sample for the JMML panel using mutant allele burden. (see [Section 7.3.1](#))
- h. Complete an age-appropriate ophthalmologic examination with a fundoscopic evaluation that avoids any sedation to be performed by an ophthalmologist at the end of Cycle 4 and every 12 weeks after while on study. Snellen examination (if age appropriate as determined by the investigator). See [Section 4.1.6](#).
- i. Bone marrow; to be collected on every odd numbered cycle only (i.e. cycle 3, 5, 7 etc.). **Note:** Only obtain if the bone marrow blast percentage and karyotype are the only remaining variables required to determine response classification as documented in [Appendix III](#) Tables 1 and 2
- j. ECG to be collected every 3 cycles after Cycle 2 (i.e. cycle 5, cycle 8, cycle 11)
- k. ECHO/MUGA: every 3 cycles after Cycle 2 (i.e. cycle 5, cycle 8, cycle 11)

This listing only includes evaluations necessary to answer the primary and secondary aims. OBTAIN OTHER STUDIES AS REQUIRED FOR GOOD CLINICAL CARE.

Comments

(Include any held doses, or dose modifications)

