7.1 End of Therapy & Follow-up

STUDIES TO BE OBTAINED	End of Therapy	Progressive Disease
History	X	
Physical exam with VS	X	
Ht, Wt, BSA	X	

Performance status	X	
Pregnancy test	X	
CBC, differential, platelets	X	
Electrolytes including Ca ⁺⁺ , PO ₄ , Mg ⁺⁺	X	
Creatinine, SGPT (ALT), bilirubin	X	
Total protein/albumin	X	
Bone marrow evaluation	X	
JMML panel using mutation allele burden	X	X
Genomic, Epigenomic and Functional assays*	X	X

*if the patient consented

See COG Late Effects Guidelines for recommended post treatment follow-up:

<http://www.survivorshipguidelines.org/>

Note: Follow-up data are expected to be submitted per the Case Report Forms (CRFs) schedule.

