9.3 Methods of Analysis

Response criteria are described in [Appendix III](#). A responder is defined as a patient who achieves a best response (as defined in [Section 10.2](#)) of PR or CR on the study prior to having an overall response of PD (as defined in [Section 10.2](#)); all others will be considered non-responders. The evaluation period for determination of the best response will be 12 treatment cycles. Response rates will be calculated as the percent of evaluable patients who are responders, and confidence intervals will be constructed accounting for the two-stage design.

Duration of response (Aim 1.2.5) will be defined as the time from first occurrence of PR or CR until the first occurrence of PD, death, or going off study. Patients who progress will be considered to have had an event, patients who die prior to progressing will be considered to have a competing event, and patients who go off study prior to progressing will be censored at time of last contact. The analysis will be done using the method of Gray.⁴⁵

Toxicity tables will be constructed to summarize the observed incidence by type of toxicity and grade. A patient will be counted only once for a given toxicity for the worst grade of that toxicity reported for that patient. Toxicity information recorded will include the type, severity, time of onset, time of resolution, and the probable association with the study regimen.

The analytic unit for monitoring for protocol-specific toxicities will be the patient-course: Each course where the patient receives the agent and either 1) has a protocol-specific toxicity event, or 2) receives at least 85% of their assigned dose during the cycle will be considered in the analysis. If there is strong evidence (posterior probability of at least 70% with at least 2 observed toxicities) that there is a per course protocol-specific toxicity probability of more than 20%, such information will be presented to the DSMC.

We will use a Bayesian rule to monitor for protocol-specific toxicities. We will assume a beta prior distribution with $\alpha = 0.52$ and $\beta = 2.08$. At least once per month, we will calculate the posterior probability (given the data) that the probability of protocol-specific toxicity exceeds the 20% threshold:

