$$P(p_{\text{protocol-specific toxicities}} > 20\% | \text{Data}) = \frac{\int_{0.2}^1 \binom{n}{x} p^x (1-p)^{n-x} \cdot \frac{\Gamma(2.6)}{\Gamma(0.52)\Gamma(2.08)} \cdot p^{-0.48} (1-p)^{1.08} dp}{\int_0^1 \binom{n}{x} q^x (1-q)^{n-x} \cdot \frac{\Gamma(2.6)}{\Gamma(0.52)\Gamma(2.08)} \cdot q^{-0.48} (1-q)^{1.08} dq}$$

Here n is the number of protocol-specific toxicity-evaluable cycles and x is the number of such cycles on which a protocol-specific toxicity event is observed. Examples of situations in which this rule will indicate protocol-specific toxicities have been noted and are presented below:

Number of failures	Number of patient-cycles
2	6
3	10
4	14
5	19
6	23
7	28
8	32
9	37
10	41
11	46
12	51
13	55
14	60

Protocol-specific toxicities of interest include rash, diarrhea, ejection fraction changes, hypertension, prolonged QTc, pneumonitis, visual changes, ALT increase, AST increase, and bilirubin increase.

If there is strong evidence (posterior probability of at least 70% with at least 2 observed toxicities) that there is a per course protocol-specific toxicity probability of more than 20%, such information will be presented to the DSMC.

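### Section 5.4.7 limits ECHO/MUGA after Cycle 2 to clinical need, but Section 4.4.2 and the Cycle 3+ delivery map schedule it at Cycles 5, 8 and 11

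*Combined protocol and SAP*

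**What the plan says.** Section 5.4.7 makes ECHO/MUGA mandatory at baseline and at the end of Cycles 1 and 2. It then adds: "Any ECHO/MUGAs thereafter should be done only if clinically indicated".

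Section 4.4.2, item k, reads: "ECHO/MUGA: every 3 cycles after Cycle 2 (i.e. cycle 5, cycle 8, cycle 11". The list is headed "4.4.2 Required Observations in All Subsequent Cycles". The Cycle 3+ therapy delivery map (4.4.1) places item k on Day 28. The map itself gives no cycle numbers for item k; these come from the item.

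Three other places bear on the point:

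- Section 7.1, under "STUDIES TO BE OBTAINED", lists no ECHO/MUGA at end of therapy or at progression.
- Section 9.3 states: "Protocol-specific toxicities of interest include rash, diarrhea, ejection fraction changes, hypertension, prolonged QTc, pneumonitis, visual changes". It adds liver chemistry changes to that list. A cycle with a listed event counts in the monitoring rule, and so does a cycle in which the patient "receives at least 85% of their assigned dose during the cycle will be considered in the analysis".
- Section 2.3.1 reports that, across adult trials at the recommended dose, "approximately 11% of patients have developed evidence of decrease in LVEF below the institutional lower limits of normal", together with an absolute fall of at least 10% from baseline.

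**The concern.** Limiting later scans to cases of clinical need excludes routine scans, so the two sections give opposite instructions for the same patients. Section 5.4.7 is where a site looks for guidance on ejection fraction.

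What is at stake is detection of silent cardiac toxicity in children treated for up to a year. The asymptomatic row of the 5.4.7 table acts on a measured fall in a patient without symptoms. Such a patient may give no clinical reason for a scan, so the timing sentence undercuts the rule that follows it. Section 5.1.1 makes Grade 2 left ventricular ejection fraction disease dose-limiting, and Section 11.10 asks for Grade 1 and 2 falls to be reported. Neither can be met reliably for silent events without imaging.

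**Working it through.** No statistical figure in the plan is in question, so this is a comparison of texts plus calendar arithmetic.

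**Inputs.** Cycles last 28 days, with up to 12 cycles (experimental design schema; 4.1). End-of-cycle studies are placed at day 28 × cycle number, baseline at day 0, and cycles are assumed to run without delay.

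**Schedule over 12 cycles (12 × 28 = 336 days)**

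| | 4.4.2 with the Cycle 1 and 2 maps | 5.4.7 |
|---|---|---|
| Study days | 0, 28, 56, 140, 224, 308 | 0, 28, 56 |
| Scheduled studies | 6 | 3 |
| Gaps in days, including to day 336 | 28, 28, 84, 84, 84, 28 | 28, 28, 280 |
| Longest gap | 84 | 336 − 56 = 280 |

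For a patient who completes 8 cycles, the longest gap is 84 days against 224 − 56 = 168 days.

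**Scheduled studies after Cycle 2, by cycles completed**

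| Cycles completed | 4.4.2 | 5.4.7 |
|---|---|---|
| up to 4 | 0 | 0 |
| 5 to 7 | 1 | 0 |
| 8 to 10 | 2 | 0 |
| 11 to 12 | 3 | 0 |

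The conflict therefore reaches only patients who complete Cycle 5.

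**Monitoring rule in 9.3.** Cycles with an end-of-cycle study are 1, 2, 5, 8 and 11 under 4.4.2 (5/12 = 42%) and 1 and 2 under 5.4.7 (2/12 = 17%). As an upper bound, take all 20 patients of the Simon design completing 12 cycles, which is 20 × 12 = 240 patient-cycles. Imaged cycles are then 20 × 5 = 100 against 20 × 2 = 40. Cycles without a scheduled measurement are 240 − 100 = 140 (58%) against 240 − 40 = 200 (83%). Most cycles have no scheduled measurement under either schedule. The conflict accounts for at most 60 of the 240.

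**Which schedule the protocol intends.** Section 4.4.2 says its list is confined to evaluations needed for the primary and secondary aims, and toxicity is secondary aim 1.2.1. After a restart following an ejection fraction fall, 5.4.7 itself calls for repeat imaging at 2, 4, 8 and 12 weeks and then says "continue in intervals of 12 weeks thereafter". That is the same spacing as 3 × 28 = 84 days in item k. Both facts favour 4.4.2.

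**The case against.** The strongest reply is that sites work from the delivery map. It lists the study on Day 28 under required observations, so most sites would scan anyway. That stands: lost scans are a possibility, not the expected outcome. Physical examinations continue every cycle and ECGs at Cycles 5, 8 and 11, and either may prompt a scan. Neither measures ejection fraction. A patient restarted after a fall is closely re-imaged under 5.4.7 in any case.

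A second reply is that the delivery maps refer to Section 3.2.5 for the criteria to start each cycle, and 3.2.5.4 includes cardiac function. Section 4.1.3, however, ties those criteria to the assessments on the maps, speaks of laboratory parameters, and schedules no scan. It does not resolve the conflict.

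Two stronger readings are tempting but not supported:

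- A reader might infer that the conflict undermines the Bayesian toxicity rule. Most of the under-ascertainment comes from the 9.3 denominator and would remain after the correction. Ejection fraction is one of ten pooled toxicities, and crossing the threshold only brings the information to the DSMC.
- A reader might apply the adult 11% to 20 children (0.11 × 20 = 2.2) and call those falls missed. The documents give no timing for the adult falls, no paediatric JMML rate, and no indication of how many sites would follow 5.4.7.

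**Conclusion.** This is an internal inconsistency in a safety schedule, wrong as written in the current text, and it should be corrected. For a patient completing 12 cycles under 5.4.7, the cost is 3 scheduled studies and a longest unscheduled stretch of 280 days instead of 84. These figures assume 28-day cycles without delay and a site that follows 5.4.7 to the letter. Where sites follow different sections, detection of ejection fraction changes would differ between them. The number of falls missed and the effect on the 9.3 rule cannot be sized. The Simon two-stage design is untouched.

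A reader might also infer a second conflict of the same kind, between the 14-day hold limit in 5.3 and the 4-week limit in 5.4.7. I do not claim it. Section 5.1.1 refers the reader to 5.4 for managing toxicities of special interest, so the specific table is naturally read as governing.

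**What to change.** In 5.4.7, replace the two sentences on timing with one: *ECHO or MUGA is required at baseline and at the end of Cycles 1, 2, 5, 8 and 11 (see Section 4.4.2), and additionally whenever there is a clinical indication.* Leave 4.4.2 and the delivery map as they are.

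The cost is a wording amendment with IRB review and a notice to sites. It adds no procedure beyond those 4.4.2 already requires. A site now following 5.4.7 would do up to 3 more studies per patient. Sample size, type I error (0.069) and power (0.882) do not change.

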5.4.8. Trametinib Dose Modification for QTc Prolongation

Trametinib Withholding and Stopping Criteria for QTc Prolongation	
QTc Prolongation ^a	Action and Dose Modification

 QTcB >500 msec 	
 Interrupt study treatment until QTcB prolongation resolves to Grade 1 or baseline. Test serum potassium, calcium, phosphorus, and magnesium. If abnormal, correct per routine clinical practice to within normal limits. Review concomitant medication usage for a prolonged QTc. Restart at current dose.^b If the event recurs after restarting, permanently discontinue study treatment.
Abbreviations: msec = milliseconds; QTcB = QT interval on electrocardiogram corrected using Bazett's formula ^a Based on average QTc value of triplicate ECGs. For example, if an ECG demonstrates a prolonged QT interval, obtain two or more ECGs over a brief period, and then use the averaged QTc values of the three ECGs to determine if study treatments should be interrupted or discontinued. ^b if the QTc prolongation resolves to Grade 1 or baseline, the subject may resume study treatment if the investigator determines that the subject will benefit from further treatment.	

